7.2.5 Antiviral therapies

Antiviral therapies, including those used for reasons other than CMV infection will be summarized by reason for use.

All subjects should receive 100 days of prophylactic valganciclovir or ganciclovir continuously starting within 10 days of transplant. The numbers of days on the prophylaxis will be summarized by treatment for the SAF.

7.2.6 Transplant Information

The following characteristics of the transplant procedure will be summarized by treatment for the SAF.

- Use of anti-thymocyte globulin (ATG) (Yes/No)
- Type of transplant (living donor & ATG=Yes/ living donor & ATG=No/ deceased donor & ATG=Yes/ deceased donor & ATG=No)
- Recipient and donor relatedness (living related donor, living unrelated donor, deceased donor)

- Donor demographics (age, gender, race)
- Recipient and donor HLA typing
- HLA cross match at time of transplant (see [Appendix 1](#) for how the cross match is determined)
- Recipient and donor ABO types
- Recipient and donor Hepatitis B virus, Hepatitis C virus, and Epstein-Barr Virus serostatus, if available, and HCV PCR RNA, (if available)
- Organ preservation method

7.3 Study Drug

Descriptive statistics for total number of injections subject received and the time from first dose to final dose of study drug will be presented by treatment. Furthermore, the number and percentage of subjects receiving study drug injection at each scheduled dose will be presented by treatment. These summaries will be produced for the SAF.

7.4 Analysis of Efficacy

7.4.1 Analysis of Primary Endpoint

7.4.1.1 Primary Analysis of Primary Efficacy Endpoint

The primary efficacy endpoint is the proportion of subjects with CMV viremia which is defined as plasma viral load ≥ 1000 IU/mL assessed by central assay through one year post first Study Drug injection. CMV viral load tests are scheduled once every 2 weeks for the first 8 tests starting 100 days from transplant and subsequently once per month for 7 more tests. In addition, a subject may have unscheduled tests (suspect CMV syndrome or CMV tissue-invasive disease) by the local laboratory so that the subject can be treated promptly with antiviral therapy (AVT) if needed. Everytime a local laboratory is performed, the sample should also be sent to the central laboratory for assessment. The CMV viral load collected from the central laboratory after first injection (Day 1) through day 380 ($=365+14+1$) that were collected as scheduled or unscheduled assessments will be utilized.

A patient who discontinue the study without a positive CMV viral load will be imputed as having a CMV viremia. A patient who has more than one time with viral load ≥ 1000 IU/mL by central assay will be counted once in this summary. Any unscheduled central laboratory values within the window will be included.

A Cochran-Mantel-Haenszel (CMH) test at the 1-sided 5% level stratified by use of anti-thymocyte globulin (ATG) and by receipt of a kidney from a living or deceased donor will be used to analyze the primary endpoint of CMV incidence rate.

The null and alternative hypotheses for this comparison are:

H0: Common Odds Ratio = 1.

H1: Common Odds Ratio < 1.

The odds ratio is defined as the ratio of odds of viremia in the ASP0113 group to that in the placebo group. The 1-sided p-value with the 2-sided exact 90% confidence interval for the

common odds ratio will be calculated (in SAS specifying the comor option in the exact statement of proc freq).

The primary analysis will be conducted for the FAS population.

7.4.1.2 Sensitivity Analysis for Primary Efficacy Endpoint

Three sensitivity analyses for the primary efficacy endpoint will be conducted.

An analysis identical to the primary analysis described in Section 7.4.1.1 will be repeated:

- A subject with two consecutive missing central laboratory CMV assessments
- Composite endpoint of either CMV viral load ≥ 1000 IU/mL by central laboratory OR use of AVT per adjudication

The third sensitivity analysis will be conducted using the Kaplan-Meier method for the FAS population. Time to first occurrence of a patient's CMV viremia will be included and treatment groups will be compared using a log-rank test.

Time to first event (in days) is calculated for each subject by taking the difference between the date of first study drug injection and the date of first event during the primary study period plus 1. If a subject does not have the event of interest through Day 380 the subject will be censored at Day 380. If a subject discontinues the study (or lost to follow up) before Day 380 then the subject will be considered as censored at last assessment. If the event occurs outside the primary study period it will not be counted for the analysis.

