The incidence endpoints will be each analyzed using CMH method described in 7.4.1.1.

The survival endpoints (time to first event) will be each analyzed in a Cox proportional hazards model. The Cox model will include the randomization factors. The common hazard ratio and confidence limits will be estimated. The 1-sided p-values for testing the hypothesis that the hazard ratio is equal to unity will be calculated. The Kaplan-Meier estimates of survival curves for the treatment groups will be displayed.

Peak CMV viral load and AUC through one year post first Study Drug injection will be compared using Wilcoxon rank-sum tests.

The change from baseline to last visit in estimated glomerular filtration rate (eGFR) and the changes in Health Economic and Outcomes Research (HEOR) scores and patient reported quality of life scores will be each compared between treatment groups using an ANCOVA model with the change in score as the outcome and the treatment as the factor and baseline value as the covariate.

All analyses of exploratory endpoints will be performed using the FAS.

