4 SAMPLE SIZE

In a recent study of prophylactic valganciclovir given at 900 mg/day for 100 days to donor CMV-seropositive/recipient CMV seronegative (D+R-) kidney transplant recipients [Humar, 2006], CMV viremia, defined as CMV viral load \geq 1000 IU/mL, was seen through one year in 83 of 163 subjects [50.9%, 95% CI = (43.0%, 58.8%)]. In another study [Couzi, 2012], CMV infection, defined as two consecutive positive Polymerase Chain Reaction (PCR) assay results, was seen in 11 of 32 subjects (34.4%, 95% Confidence Interval (CI) = (18.6%, 63.2%)), respectively. Pooled from these two studies by weighted average, it is estimated that placebo rate is 46% (70% weight on Humar's result). A sample size of 64 subjects per arm will allow the study to have 80% power to detect a reduction in CMV viremia to 25% due to ASP0113 at 52 weeks using a 1-sided Chi-square test with a type 1 error rate of 5%. To allow for drop-out (randomized but not evaluable), 70 subjects per arm will be enrolled for a total sample size of 140 subjects.

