7 STATISTICAL METHODOLOGY

7.1 General Considerations

All statistical analyses and summary information will be generated according to this analysis plan and any deviations from this plan will be documented in the clinical study report. Any numerical rounding should be performed at the end of calculations. The p-values will be displayed with 3 decimal places. Statistical significance will be determined prior to rounding the p-value.

For continuous variables, descriptive statistics will include the number of subjects (n), mean, standard deviation, median, minimum and maximum. Frequencies and percentages will be displayed for categorical data. Percentages by categories will be based on the number of subjects with no missing data thus the percentages will add up to 100%. Baseline will be the last non-missing value on or prior to first study drug unless otherwise specified.

All efficacy comparisons will be tested at the 1-sided 0.05 significance level. Confidence intervals for efficacy estimates, if provided, will be constructed at 2-sided 90% level.

All data processing, summarization, and analyses will be performed using SAS® Version 9.1.3 or higher on Unix.

This SAP includes the data analysis for the primary study period (ie, 1-year post first study drug injection) which is defined as data collected through day 380 (=365+14+1 day). Certain data summary will consider analysis window as specified in each section. The long-term follow-up period is not covered by this SAP and will be managed in a separate SAP.

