7.4.3 Analysis of Exploratory Endpoints

The analyses of all exploratory variables defined in Section [6.1.3](#) will be performed on the FAS. Each of these variables will be summarized by treatment. If the endpoint is measured at different visits, the variable will be summarized by treatment at each visit and at Final Visit unless stated specifically otherwise.

Comparisons between treatment groups for the following binary variables will be tested using the exact CMH method as described in Section [7.4.1.1](#)

- viral resistance to ganciclovir or valganciclovir
- biopsy-proven acute rejection (BPAR)
- clinically treated acute graft rejection

Viral resistance to ganciclovir or valganciclovir is confirmed by central laboratory. Biopsy proven acute rejection (BPAR) is captured in the CRFs. For acute antibody mediated

rejection with Banff grade ≥ 1 or for T-cell mediated rejection with grade $\geq 1a$ BPAR will be “yes”. Clinically treated acute graft rejection will be from the CRF.

The time to the first adjudicated CMV disease, including CMV syndrome and CMV tissue-invasive disease will be analyzed using the same method as described in the third sensitivity analysis in Section [7.4.1.2](#)

The following count variables may be affected by duration of follow-up which is the time of last assessment from first injection plus 1. Therefore, each of the variable will be compared between treatments using Poisson regression with treatment and randomization stratum as factors offset by follow-up time. The risk ratio, 1-sided 5% p value and the 90% confidence interval for the risk ratio will be presented.

- Number of opportunistic infections other than CMV
- Number of episodes of CMV viral load of ≥ 1000 IU/mL by central assay
- Number of episodes of adjudicated CMV-associated disease, including CMV syndrome and CMV tissue-invasive disease

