7.9 Handling of Missing Data, Outliers, Visit Windows, and Other Information

7.9.1 Missing Data

In the analysis of the primary endpoint, subjects who are lost to follow-up will be imputed as having viremia. Otherwise, viremia will not be imputed. Only observed viral loads from central labs meeting the definition of viremia will be counted.

Time to event variables will be considered censored at the time of the last assessment. Time to the first protocol-defined CMV viremia will be considered censored at the time of the last recorded central laboratory CMV measurement.

The start and stop dates of AEs and concomitant medication will be imputed to allocate the concomitant medication and AEs to a treatment group, in addition to determining whether an AE is/is not treatment emergent. Listings of the AEs and concomitant medications will present the actual partial dates; imputed dates will not be shown.

In case of missing partial start and stop dates for concomitant medications, the following rules will be used:

If start date is missing or partial:

- if month is missing, use January
- if day is missing, use the first day of the month under consideration
- if year is missing, use year of the informed consent date
- if entire date is missing, use informed consent date

If stop date is missing or partial:

- if month is missing, use December
- if day is missing, use the last day of the month under consideration
- if year or the entire date is missing, set to December 31st, 2099

If the imputed start date is after the stop date, then the imputed start date will be one day prior to the stop date.

For AEs, a missing or incomplete onset date will be imputed according to the following conventions for the purpose of defining TEAE.

- 1) Missing year, the AE will be count as TEAE
- 2) Missing month, the AE will be counted as TEAE if the year is equal to the consent year or one year later.
- 3) Missing date, using the last date of the month to determine TEAE.

No imputation of missing data for other variables will be done.

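### The two time-to-event analyses lose the protocol's Cox model: the SAP gives a log-rank test with no stratification stated and no hazard ratio, and its censoring rules disagree for event-free completers

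*SAP*

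**What the plan says.** Protocol 7.4.3 analyses every time-to-first-event endpoint with a Cox proportional hazards model, and "The Cox model will include the randomization factors". It asks for a hazard ratio with confidence limits, a 1-sided p-value and Kaplan-Meier curves. The synopsis says the same.

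SAP 7.4.1.2 makes time to first viremia the third sensitivity analysis of the primary endpoint. It uses Kaplan-Meier, and "treatment groups will be compared using a log-rank test". SAP 6.1.3 also lists time to first viremia as an exploratory endpoint. Time to first adjudicated CMV disease "will be analyzed using the same method as described in the third sensitivity analysis" (SAP 7.4.3). A Cox model and a hazard ratio appear nowhere in the SAP.

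Two general rules still apply to these tests: "All efficacy comparisons will be tested at the 1-sided 0.05 significance level", and "Confidence intervals for efficacy estimates, if provided, will be constructed at 2-sided 90% level" (SAP 7.1).

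On censoring, SAP 7.4.1.2 puts a subject with no event through Day 380 at Day 380, and a subject who discontinues earlier at the last assessment. SAP 7.9.1 censors time-to-event variables in general at the last assessment, and adds: "Time to the first protocol-defined CMV viremia will be considered censored at the time of the last recorded central laboratory CMV measurement".

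**The concern.** Randomization is stratified by ATG use and by living or deceased donor. Where those factors predict viremia, a test that ignores them is conservative and gives up some power.

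The missing estimate matters more. The primary analysis counts subjects who discontinue without a positive result as viremic. The first two sensitivity analyses repeat the primary analysis with a changed event definition, so they keep that imputation. The third is the only one that censors dropouts instead. It is the natural check on the imputation, yet it yields no hazard ratio and interval to set beside the primary odds ratio.

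On censoring, two programmers following different sections of the same SAP would build different datasets for completers.

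**Working it through.** **Stratification and estimate, section by section.** The SAP names the strata for the CMH test (7.4.1.1) and for the Poisson regression, the rank tests of peak and cumulative viral load, and the eGFR ANCOVA (7.4.3). For the viral-load rank tests and the ANCOVA it adds an adjustment that the protocol did not have. For the log-rank test it names none, although the protocol did adjust there. An unstratified test is therefore the natural reading, but it is read from silence.

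**The plan's own figure.** Inputs from SAP section 4: "it is estimated that placebo rate is 46" percent, and "A sample size of 64 subjects per arm will allow the study to have 80% power to detect a reduction in CMV viremia to 25" percent, 1-sided 5%. With pooled variance and mean rate 0.355:

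n = [1.645·√(2·0.355·0.645) + 0.842·√(0.46·0.54 + 0.25·0.75)]² / 0.21² = (1.113 + 0.556)² / 0.0441 ≈ 63.2, so 64 per arm (power 80.5%). The figure reproduces and is not in dispute.

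**What the time-to-event analysis could report.** The documents give no event target, so proportional hazards is assumed.
- Implied hazard ratio: ln(0.75)/ln(0.54) = 0.467.
- Events for 80% power (Schoenfeld): 4·(1.645 + 0.842)²/(ln 0.467)² = 43. Freedman's formula gives 47.
- Expected events: 70·(0.46 + 0.25) = 49.7, ignoring dropout; power 85%.
- Approximate 90% interval: the standard error of the log hazard ratio is 2/√49.7 = 0.284, so the limits are 0.467·exp(±1.645·0.284), or 0.29 to 0.74. This is the kind of statement that the SAP as written does not ask for.

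**Cost of not stratifying.** Simulation at 46% against 25%, 1-sided 5%, 70 per arm, 1,000 runs per row. Assumptions not in the documents: four equal strata, 10% dropout, constant hazard from study Day 60, and the same hazard ratio for each stratification factor. Day 380 censoring rule:

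| Hazard ratio per factor | Power, unstratified | Power, stratified | Size, unstratified | Size, stratified |
|---|---|---|---|---|
| 1 | 82.0% | 82.1% | 4.4% | 4.4% |
| 1.5 | 83.1% | 83.6% | 5.4% | 5.8% |
| 2 | 83.2% | 85.9% | 4.8% | 4.5% |
| 3 | 86.5% | 91.2% | 2.8% | 4.6% |

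The Monte Carlo standard error of a 5% size is √(0.05·0.95/1000) = 0.7 points. Only the 2.8% departs clearly from nominal. A second simulation with unequal strata (1,500 runs) gave 83.1%, 83.1% and 84.2% unstratified against 83.2%, 83.4% and 86.1% stratified for factor hazard ratios of 1, 1.5 and 2, which are gains of 0.1, 0.3 and 1.9 points.

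**Censoring.** For subjects who discontinue, both sections point to the last assessment; SAP 7.9.1 only narrows it for viremia to the last central measurement. For event-free completers the sections conflict. The Visit 13 analysis window in SAP 7.9.3 is Day 352 to 380, so the gap is 380 − 380 = 0 to 380 − 352 = 28 days, and more if late samples are missed. The rule alters the risk set only at event times after a completer's last sample, so few events are touched. In the 1,000-run simulation, switching rules moved the test statistic by about 0.04 on average (at most about 0.4) and changed the 1-sided decision in 0.1% to 1.0% of runs. Visit 13 there fell on Day 361 to 380 and no late samples were missed, so the run covers gaps up to 19 days.

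**The case against.** The strongest reply is that little hangs on this. Time to disease is exploratory, and time to viremia is a sensitivity analysis and an exploratory endpoint. The primary test is stratified, and its common odds ratio has an exact 90% interval. The 1-sided 5% level carries over through SAP 7.1. Any conservatism carries no false-positive risk. All of that stands, and it limits the weight of the point without removing it.

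Five stronger readings are tempting, and the documents do not support them:
- *That the SAP made an unrecorded change.* Appendix 4 lists changes since the approved SAP of 15 April 2014, not departures from the protocol. That version may already have used the log-rank test. What can be said is that the current SAP gives no reason. The commitments in protocol section 7 and SAP section 1 to explain changes in the study report concern departures from the SAP, so they would not capture this one.
- *That the SAP chose an unstratified test.* It is silent.
- *That the censoring conflict covers all event-free subjects.* SAP 7.4.1.2 already censors discontinuers at the last assessment.
- *That the third sensitivity analysis shows nothing about size.* Kaplan-Meier estimates will show the curves. What is missing is a summary effect with an interval.
- *That the power loss is large.* Taking 46% against 30% with strata rates from 17% to 77% gives 65.4% against 73.3%. But 30% is not a design rate: SAP Appendix 3 pairs 46% with 46, 41, 34 and 25%. The documents give no rates by stratum.

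**Conclusion.** The point holds as a consistency gap with a cheap remedy. The SAP leaves out the protocol's adjusted Cox model and hazard ratio for both time-to-event endpoints without giving a reason, and it has two censoring rules for event-free completers. The first part rests on the text alone and is the main part.

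The power effect rests on assumed strata effects. At 46% against 25% it is about 0 to 2 points for factor hazard ratios of 1 to 2 (2.7 points in the equal-strata run at 2). It is between 4 and 5 points for ratios of 3, where the unstratified test has a size of about 3%. The censoring conflict is numerically small. The primary CMH conclusion does not change.

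**What to change.** In SAP 7.4.1.2, with the cross-reference in 7.4.3:
- Restore the Cox model with ATG use and donor type for both endpoints, reporting the hazard ratio, 2-sided 90% interval and 1-sided p-value.
- State that the log-rank test is stratified by the same two factors.

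In SAP 7.4.1.2 and 7.9.1, give one censoring rule per endpoint:
- Viremia: the last central viral load on or before Day 380, since viremia can be seen only at a central sample.
- Adjudicated disease: the last assessment on or before Day 380. A viral-load date does not suit a clinical event judged by committee.

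Record the change and its reason in Appendix 4. The cost is a few sentences and minor programming before unblinding, with no new data. Stratifying cost no meaningful power in any scenario run: under the Day 380 rule it never lost power, and under the last-sample rule the differences against it were within simulation error.

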7.4.1.3 Subgroup Analysis of Primary Efficacy Endpoint

Subgroup analysis on the primary efficacy endpoint will be performed with a logistic model including treatment, subgroup, and treatment by subgroup interaction as explanatory variables. A subgroup with a level that has fewer than 10 patients within any treatment group, the level will be excluded from the interaction test while descriptive statistics will be provided. If none or only one level of the subgroup meets the 10-subject criterion no subgroup analysis will be performed. The proportion, odds ratio per subgroup factor and its 2-sided 90% confidence intervals will be calculated. As this is a phase 2 study and the interaction test between the treatment group and the subgroup factors should be interpreted with a caution, the p-value from the interaction test will be compared to 0.15.

The subgroup analysis will be performed for the FAS according to:

- levels of randomization strata
- use of ATG, alemtuzumab, or rituximab after randomization
- use of ATG after randomization
- use of alemtuzumab after randomization
- use of rituximab after randomization
- use of alemtuzumab or ATG after randomization
- kidney preservation method (cold, PUMP)
- age group (<65, ≥ 65)
- race (white, black, other)

- gender (male, female).

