3.3 Randomization

At the Screening Visit, after the Informed Consent Form (ICF) has been signed, site staff will access the IRT system, enter the subject's required information, and the subject will receive a subject number assignment through the IRT for use throughout the study.

Subjects who subsequently meet the inclusion/exclusion criteria will be randomly assigned to receive either ASP0113 or placebo. The randomization to treatment will be equally allocated (i.e., 1:1) and stratified by the use of anti-thymocyte globulin and by receipt of a kidney from a living or deceased donor. The IRT vendor will generate the randomization schedule. To obtain the randomized treatment assignment for a subject, the pharmacist or designee will utilize an IRT system, which is available seven days a week, 24 hours a day.

Randomization is to be done after the completion of the Screening period, and at least 30 days \pm 3 after transplant day (Day 0). After submitting required information about the eligible subject, the drug kit number assignment will be provided.

Study Drug assignment will remain blinded to all site staff except the pharmacist and designated staff administering the Study Drug.

If a subject is randomized but does not receive Study Drug, the kit number will not be used again. In this instance, the treatment assignment should only be known by the pharmacist and designated staff (i.e., the blind must be maintained as it is with all other subjects).

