Classifications of opportunistic infections other than CMV: Any TEAE with the following classifications will be considered and decided by the medical and safety officers of the study team before unblinding case by case if it is an opportunistic infection: (1) SOC: Renal and Urinary disorders and HLGT= Viral infectious disorders, Chlamydial Infections disorder, Mycobacterial infectious disorders, Fungal infectious disorders, Bacterial infectious disorders, Protozoal infectious disorders; (2) SOC: Renal and Urinary disorders and HLT= Genitourinary tract inflammation and infection NEC, Bladder infections and inflammations, Renal infections and inflammation, Urethral infections and inflammations.

Count episodes of the protocol defined CMV viremia:

An episode starts with CMV viral load ≥ 1000 IU/mL by central assay and ends with two consecutive CMV viral load < 1000 IU/mL by central assay separated by at least one week in time. An episode will not be counted if it starts outside the primary study Period.

The ordinal variables below assessed by the central laboratory will be compared between treatments using the stratum-adjusted Wilcoxon rank-sum test. This test is implemented in SAS Proc Freq using the CMH2 option for tests based on row mean scores and SCORES=MODRIDIT option for use of modified standardized rank score within strata:

- Peak CMV viral load
- Cumulative viral load

Calculation of cumulative viral load:

Using the linear trapezoidal rule to calculate the area under the viral load over time curve (AUC) divided by the length of time for each subject.

The eGFR and its change from baseline will be summarized by treatment at each visit and at final visit. The change from baseline to final visit will be compared using analysis of

covariance (ANCOVA) with treatment and randomization stratum as factors and baseline value as a covariate.

Calculation of eGFR:

$$186 \times \text{serum creatinine}^{-1.154} \times \text{age}^{-0.203} \times [1.212 \text{ if Black}] \times [0.742 \text{ if Female}] ,$$

where serum creatinine is in mg/dL and age in years. The value in either bracket is 1 if the stated condition is not met. If serum creatinine is in SI units (mmol/L) instead of the US units (mg/dL) then its value needs to be converted to the US units first by multiplying a factor of 1/88.4.

Data from KTQ and SF-12 will be listed without any analysis.

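### The subgroup model for the primary endpoint omits the two randomization factors; if these predict viremia, subgroup odds ratios lie somewhat nearer 1 than the stratified result and lose a little power

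*SAP*

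**What the plan says.** SAP 3.3 sets the allocation: "The randomization to treatment will be equally allocated (i.e., 1:1) and stratified by the use of anti-thymocyte globulin" and by living or deceased donor. SAP 7.4.1.1 carries both factors into the primary analysis, a CMH test "stratified by use of anti-thymocyte globulin (ATG) and by receipt of a kidney from a living or deceased donor". SAP 7.4.2 uses the same method for the secondary endpoints. The randomization strata also enter the Poisson models, the rank tests for peak and cumulative viral load and the eGFR analysis of covariance (SAP 7.4.3), and the repeated-measures immunogenicity model (SAP 7.4.4).

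SAP 7.4.1.3 differs. It specifies "a logistic model including treatment, subgroup, and treatment by subgroup interaction as explanatory variables" and names no other term. The first subgroup on its list is "levels of randomization strata". The others are immunosuppressant use after randomization, kidney preservation method, age, race and gender. On sparse levels it says: "A subgroup with a level that has fewer than 10 patients within any treatment group, the level will be excluded from the interaction test". On the decision rule: "the p-value from the interaction test will be compared to 0.15". Protocol 7.4.1.3 plans only a Breslow-Day test across the strata and defines no subgroup model, so it does not settle the question.

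**The concern.** There are two separate mechanisms, and both depend on ATG use or donor type being related to viremia.

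- **Scale.** Odds ratios are non-collapsible. When a prognostic factor is left out of a logistic model, the treatment odds ratio moves toward 1 even if the arms are perfectly balanced on that factor. The subgroup odds ratios would then be marginal, while the overall result beside them is conditional on the strata.
- **Chance imbalance.** Stratified randomization balances the two factors over the whole trial, not within an age, sex, race or preservation-method level. Any imbalance inside a level passes into that level's unadjusted odds ratio.

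At stake is how the subgroup table is read. A level may look slightly weaker than the overall result for reasons unrelated to the subgroup, and some precision already paid for by the stratification goes unused.

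**Working it through.** **Inputs.** From SAP section 4: placebo rate 46%, ASP0113 rate 25%, 1-sided 5% test, 64 per arm for 80% power, 70 per arm enrolled. From SAP 7.4.1.3: at least 10 per arm per level and an interaction threshold of 0.15. Assumed, because the documents give no figures: the prevalence of each factor, its odds ratio g for viremia, and the subgroup split.

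**1. The plan's own figure.** With p̄ = 0.355, n = [1.645·√(2·0.355·0.645) + 0.842·√(0.46·0.54 + 0.25·0.75)]² / 0.21² = (1.113 + 0.556)² / 0.0441 ≈ 63.2. This rounds up to 64 and agrees with the SAP.

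**2. Planning odds ratio.** (0.25 × 0.54) / (0.75 × 0.46) = 0.391, with log −0.938. The planned rates are overall rates, so this is a marginal odds ratio.

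**3. Conditional odds ratio at the same overall rates.** Give each factor prevalence 50% and odds ratio g. For each arm, solve for the intercept b so that the average over the four strata of expit(b + stratum effect) equals 0.46 or 0.25. The conditional odds ratio is exp(b₁ − b₀). Large-sample power in a half-sample level (32 per arm) is Φ(|log OR|/SE − 1.645).

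| g, both factors | Conditional OR | Unadjusted log OR as share of adjusted | SE adjusted / unadjusted | Power adjusted / unadjusted |
|---|---|---|---|---|
| 1 | 0.391 | 100% | 0.541 / 0.541 | 53.6% / 53.6% |
| 1.5 | 0.385 | 98% | 0.546 / 0.541 | 54.1% / 53.6% |
| 2 | 0.372 | 95% | 0.557 / 0.541 | 55.1% / 53.6% |
| 3 | 0.347 | 89% | 0.580 / 0.541 | 57.1% / 53.6% |

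The unadjusted standard error is the smaller one, so the lost power comes from attenuation and not from wider intervals.

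**4. Simulated power in a subgroup level**, with a common treatment effect and the overall rates held at 46% and 25%:

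| Per arm, level | Factor odds ratios | Unadjusted | Adjusted |
|---|---|---|---|
| 64, half | 1.5, 1.5 | 0.541 | 0.552 |
| 64, half | 2, 2 | 0.538 | 0.562 |
| 64, half | 3, 3 | 0.559 | 0.598 |
| 70, half | 1, 1 | 0.574 | 0.579 |
| 70, half | 2.5, 2 | 0.569 | 0.597 |
| 70, 30% | 2.5, 2 | 0.397 | 0.430 |
| 70, 30% | 4, 2 | 0.408 | 0.456 |

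The gain is about 0.5 to 1 point when the factors are absent or weak. At odds ratios of 2 to 4 it runs from 2.4 to 4.8 points, mostly 3 to 5.

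**5. Chance imbalance.** A 30% level has 0.3 × 70 = 21 per arm. With 50% ATG use, the SD of the arm difference is √(2 × 0.25/21) × √0.7 = 0.154 × 0.837 = 0.129. A gap above 20 points then lies beyond 0.20/0.129 = 1.55 SD, a two-sided probability of about 12%. To first order such a gap moves the unadjusted log odds ratio by 0.20 × ln 2.5 = 0.18 to 0.20 × ln 4 = 0.28. Simulation gave about 0.14 to 0.25, and adjustment largely removed it. The standard error in that level is √(1/(21 × 0.2484) + 1/(21 × 0.1875)) = 0.67, so the shift is roughly 0.2 to 0.4 of a standard error.

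**6. Interaction test at 0.15.** With no true interaction it rejected in 0.15 to 0.17 of trials under both models. With the effect in only one level, detection rose from 0.435 to 0.443 (g = 1.5), 0.446 to 0.466 (g = 2) and 0.437 to 0.471 (g = 3).

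**The case against.** The best case for leaving the text alone is that an unadjusted subgroup odds ratio with a 90% interval is a legitimate marginal summary. At the planned overall rates it equals 0.391, so it is not attenuated relative to the planned effect. The documents give no prognostic strength for either factor and set no power target for any subgroup. The shifts are small beside a standard error of 0.54 to 0.67, and SAP 7.4.1.3 already urges caution. Nor is this the only unstratified comparison: SAP 7.4.1.2 names no strata for its log-rank test, which SAP 7.4.3 reuses for time to CMV disease, and the by-visit Wilcoxon tests in SAP 7.4.4 are unadjusted. All of this stands, and it keeps the point minor.

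The sparsity objection is weaker. The model is fitted jointly over the levels, so the two main effects draw on up to 140 subjects and about 70 × 0.46 + 70 × 0.25 ≈ 50 events, not on one cell of 10 per arm. The model failed in at most about 0.5% of simulated trials. The warning against switching estimators from level to level is fair, and the fix allows for it.

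Three stronger readings are tempting, and the documents do not support them.

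- **That every listed subgroup is affected.** If "levels of randomization strata" means the four cells, that model already conditions on both factors. If each factor is run separately, only the other is missing.
- **That the subgroup results cannot be compared with the primary result.** Both are odds ratios for the same endpoint in the same direction, 0.391 against 0.385 to 0.347 for g of 1.5 to 3. They differ in scale, and only if the factors are prognostic.
- **That the omission produces false subgroup differences.** The interaction test holds close to 0.15 with or without the two factors.

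**Conclusion.** The omission is real, and the SAP gives no reason for departing from its usual conditioning in the one model whose odds ratios will be read beside the stratified common odds ratio. Its effect is conditional. If ATG use and donor type do not predict viremia, nothing is lost. If they do, the odds ratios for subgroups other than the strata lie somewhat nearer 1 (log odds ratio 2% to 11% smaller for factor odds ratios of 1.5 to 3). They also carry within-level imbalance, and their power is lower by up to about 1 point for weak factors and mostly 3 to 5 points at odds ratios of 2 to 4. These sizes rest on assumed prognostic odds ratios, factor prevalences near 50% to 60% and subgroup levels of 30% to 50% of the trial. The primary test, the sample size and the level of the interaction test are unaffected. This is a worthwhile refinement, not a threat to the trial's conclusion.

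**What to change.** In SAP 7.4.1.3, add ATG use before randomization and donor type (living or deceased) as main-effect covariates in the jointly fitted subgroup logistic model, and omit a factor when it is itself the subgroup. ATG use after randomization is a different variable, so the covariate for ATG use before randomization stays in that model. Name one fallback now: if the model does not converge, use Firth's penalized likelihood for all levels of that subgroup, so that estimators are not mixed within a comparison. If the sponsor prefers to leave the model as it is, the section should at least state that the subgroup odds ratios are unadjusted, marginal and descriptive.

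The cost is a sentence or two of SAP text and a small programming change. Both covariates are already held for the primary analysis, and simulation shows no power penalty if they turn out not to be prognostic.
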